# **Protocol Version History**

Version Number	Date	Protocol Update Finalised By (insert name of person):	Reasons for Update
Version 1	23/04/2021	[name]	Feedback from study team
Version 2	05/05/2021	[name]	Updates from comments
Version 3	08/05/2021	[name]	Feedback from study zoom meeting
Version 4	07/09/2021	[name]	Inclusion of outcome measures ready for ethics application
Version 5	20/09/2021	[name]	Updates from comments
Version 6	22/09/2021	[name]	Feedback from study team and sponsor site.
Version 7	02/12/2021	[name]	REC feedback
Version 8	15/12/2021	[name]	Feedback from co-aplicants

# List of abbreviations

AE	Adverse Event
CI	Chief Investigator
CRF	Case Report Form
CRO	Contract Research Organisation
CSRI	Client Service Receipt Inventory (resource use questionnaire)
CST	Cognitive Stimulation Therapy
EQ-5D-5L	EuroQol 5-dimension 5-level quality of life questionnaire
GAfREC	Governance Arrangements for NHS Research Ethics
GCP	Good Clinical Practice
HRA	Health Research Authority
LD	Learning Disability
ICF	Informed Consent Form
IDMC	Independent Data Monitoring Committee
ISF	Investigator Site File
ISRCTN	International Standard Randomised Controlled Trial Number
NHS R&D	National Health Service Research & Development
NICE	National Institute of Health and Care Excellence
PI	Principal Investigator
PIS	Participant Information Sheet
PSSRU	Personal Social Services Research Unit
QA	Quality Assurance
QC	Quality Control
RCT	Randomised Controlled Trial
REC	Research Ethics Committee
SAE	Serious Adverse Event
SDV	Source Document Verification
SOP	Standard Operating Procedure
SPC	Summary of Product Characteristics
TMG	Trial Management Group

# 1 Trial personnel

See protocol cover page for Chief Investigator and Sponsor contact details.

CI: [name]

e-mail: [contact]

Statistician: [name] e-mail: [contact]

Principal Investigatior NELFT: [name]

Email:[contact]

Health Economist: [name]

Email: [contact]

Qualitative researcher lead: [name]

Email: [contact]

Research Assistant: [name]

Email:[contact]

2 Summary	
Objectives:	1. To assess the feasibility and acceptability of a randomised controlled trial of group CST for people with ID and dementia compared to Treatment as Usual. The results of this study will inform the design of a future definitive RCT.
Type of trial:	Feasibility randomised multi-site trial of group CST compared to "Treatment as usual" in participants with dementia and Learning disabilities.
Trial design and methods:	Fifty individuals with ID will be randomised to either the intervention group or control group (treatment as usual). Randomisation will occur after informed consent has been given and baseline assessments completed. Each arm will have 25 participants and be divided into five or more CST groups with up to five participants in each.
	Outcome assessments will include an assessment of cognitive functioning, adaptive functioning and quality of life in individuals with dementia and will also assess the feasibility of collecting the cost-effectiveness measures. A process evaluation will include qualitative interviews with participants, staff and carers to identify aspects of the intervention and study methods including adherence. Any direct quotations used from these interviews in the final publication will be anonymised.
Estimated total trial duration:	30 months
Planned trial sites:	North East London NHS Foundation Trust, East London NHS Foundation Trust, Camden & Islington NHS Foundation Trust, Central and North West London NHS Trust Foundation, London Community Health Care NHS Trust, and Barnet, Enfield & Haringey Mental Health Trust
Total number of	
participants planned:	50
Main inclusion/exclusion criteria:	Inclusion criteria 1. Mild or moderate Learning disabilities 2. ICD-10 diagnosis of mild or moderate dementia

Statistical methodology and analysis: As this is a feasibility study, we do not anticipate that there will be statistically significant differences in the outcome measures between the intervention and control groups. However, we will examine differences in the mean and standard deviation for the primary	•••	
 
Exclusion criteria
 
Severe Learning disabilities
 
Severe dementia
 
Visual or hearing impairment that prevents participation
 
As this is a feasibility study, we do not anticipate that there will be statistically significant differences in the outcome measures between the intervention and control groups. However, we will examine differences in the mean and standard deviation for the primary outcome (cognitive functioning) in order to calculate a sample size for a larger study.
 

---------------------------------------------------------------------------------------------------------------------------------------------------------------------------------------------------------------------------------------------------------------------------------------------------------------------------------	-----	-----------------------------------------------------------------------------------------------------------------------------------------------------------------------------------------------------------------------------------------------------------------------------------------------------------------------------------------------------------------------------------------------------------------------------------------------------------------------------------------------------------------------------------------------------

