#### 3. Feasibility Randomised Controlled Trial

This will be a single blind, pilot randomised controlled trial of CST delivered by professionals versus treatment as usual. Fifty participants will be randomised to either the intervention group or control group (treatment as usual). Randomisation will occur after baseline assessments are completed. Each arm will have 25 participants and they will be allocated to one CST group with up to five participants in each group.

The duration of the intervention will be 7 weeks. There will be assessments at baseline during the two weeks prior to randomisation, and at the end of the intervention after 8-9 weeks.

Please refer to figure 1 which shows the overall trial design.

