# **11** Statistical Considerations

#### **11.1 Statistical analysis**

Baseline characteristics will be summarized for all participants, the intervention group and control groups separately. Participants' uptake of and adherence to the intervention, as well as follow-up rates, will be summarized and presented as percentages.

Although determining differences in clinical outcomes between the arms is not the primary purpose of this trial, comparisons will be undertaken to investigate the feasibility of studying these outcomes and to calculate estimates for the likely effect sizes and 95% confidence intervals. As recommended in guidelines for good practice for the analysis of pilot studies, the focus of the results will be on the estimates of the treatment effects rather than statistical significance and as such no hypothesis testing will be undertaken. Differences between the two comparison groups will be presented in the form of an unadjusted mean difference for continuous outcomes, and an odds ratio for binary outcomes, with

their associated 95% confidence intervals. Despite the individual randomisation there is group based treatment and therefore consideration will also be made in regard to estimation of the potential intracluster correlation (ICC) coefficient. The estimation of the likely ICC will be able to guide the sample size of a future trial.

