# **11.2** Sample size calculation

This is a feasibility study with no formal power calculation. Instead, a sufficient number of participants need to be recruited in order to determine the attrition and recruitment rates and how these are related to feasibility for a full scale RCT. By setting our target sample size at 50 we will achieve adequate precision around our expected retention rate of 75% (95% confidence interval of 62-86%) to determine the feasibility going forward. Based on our previous study data we are anticipating we will have to screen a maximum of 70 people to reach our sample size.

There is no available data on the use of Cognitive Stimulation Therapy in the treatment of dementia in people with Learning disability. This sample should also provide adequate precision using a confidence interval approach which considers the likelihood of a future definitive study finding a relevant effect size.

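### The Summary feeds the observed between-arm difference into the definitive trial's sample size, although about 19 completers per arm estimate that difference only to within ±0.66 SD

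*Protocol*

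**What the plan says.** The statistical entry of the Summary (section 2) first says that significant differences are not expected, and then, with a larger study in view, that "we will examine differences in the mean and standard deviation for the primary outcome (cognitive functioning) in order to calculate a sample size". Both the difference in means and the standard deviation are therefore named as inputs to the future calculation.

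Section 11.1 plans to "calculate estimates for the likely effect sizes and 95% confidence intervals", without hypothesis tests. On the form of the comparison it says: "Differences between the two comparison groups will be presented in the form of an unadjusted mean difference for continuous outcomes". It adds that an intracluster correlation will be considered, to guide the size of a future trial.

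Section 11.2 gives one precision figure, a 95% interval of 62-86% around the expected 75% retention with 50 participants. On effect size it then says: "This sample should also provide adequate precision using a confidence interval approach which considers the likelihood of a future definitive study finding a relevant effect". No half-width, confidence level or relevant effect accompanies that sentence. Section 5 sets the allocation: "Each arm will have 25 participants".

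The protocol nowhere names a minimum important difference, or any other source, for the target difference of the definitive trial.

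**The concern.** The required sample size varies with the inverse square of the target difference, so sampling error in that difference is magnified when it is used for sizing. A study of this size estimates the SD tolerably well but the difference in means poorly. If the observed difference becomes the target, a chance high estimate gives an underpowered definitive trial. A chance low one gives a trial too large to run, and an estimate at or below zero gives no sample size at all. The assertion of adequate precision in section 11.2 may encourage that use, because it carries no number that would show a reader how wide the interval will be.

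**Working it through.** **The plan's own figure.** With 38 of 50 retained, the Agresti-Coull interval uses (38+2)/(50+4) = 0.741 and 1.96 × √(0.741 × 0.259/54) = 0.117, giving 62.4-85.8%. This agrees with the stated 62-86%, so the retention precision in section 11.2 is sound.

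**Inputs for the difference in means.**
- Total 50, 25 per arm (sections 5 and 11.2).
- Retention 75% (section 11.2): 0.75 × 50 = 37.5, about 38 completers or 19 per arm.
- Unadjusted mean difference with a 95% confidence interval (section 11.1).
- SD scaled to 1, because the protocol gives none.

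**Half-width of the 95% interval.**
- 19 per arm: SE = √(1/19 + 1/19) = 0.324 SD. With t(0.975; 36 df) = 2.028, the half-width is 2.028 × 0.324 = 0.658 SD.
- All 50 followed up: SE = √(2/25) = 0.283 SD. With t(0.975; 48 df) = 2.011, the half-width is 0.569 SD.
- Clustering in the CST arm: SE = √(DE/19 + 1/19), DE = 1 + (m − 1) × ICC. The protocol gives no ICC. Over an assumed 0.01-0.10 and group sizes m of 3.8 to 5, DE runs from 1.028 to 1.40 and the half-width from 0.66 to 0.72 SD.

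**Correct sample size for assumed true effects.** At two-sided 5% and 80% power (both assumed for the future trial), n per arm = 2 × (1.960 + 0.842)²/d² = 15.70/d².

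| Assumed true effect d | Correct n per arm |
|---|---|
| 0.3 SD | 175 |
| 0.4 SD | 99 |
| 0.5 SD | 63 |

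**Effect of one standard error.** At d = 0.4, an estimate one SE high (0.724) gives 30 per arm and one SE low (0.076) gives 2718. At d = 0.5 the corresponding figures are 24 and 507, against 63.

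**How often the sizing goes badly wrong.** Because n varies as 1/d², n falls below half the correct value when the estimate exceeds d√2. It exceeds twice the correct value, or cannot be computed, when the estimate is below d/√2. Taking the estimate as normal with SE 0.324 and the SD as known:

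| d | P(n below half) | P(n above twice, or none) | P(estimate ≤ 0) |
|---|---|---|---|
| 0.3 | P(Z > 0.124/0.324 = 0.383) = 35% | P(Z < −0.088/0.324 = −0.271) = 39% | 18% |
| 0.4 | P(Z > 0.166/0.324 = 0.511) = 30% | P(Z < −0.117/0.324 = −0.361) = 36% | 11% |
| 0.5 | P(Z > 0.207/0.324 = 0.638) = 26% | P(Z < −0.146/0.324 = −0.451) = 33% | 6% |

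The last column is part of the third. A simulation that also lets the SD be estimated on 36 degrees of freedom gives 27-35% and 32-39%, so the conclusion does not depend on treating the SD as known. The power level cancels from these probabilities and affects only the absolute n.

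**The case against.** The strongest reply is that the whole charge rests on one sentence in the Summary. Section 11 is the operative text. It plans estimation without tests, says that clinical differences are not the main purpose, and names only the ICC as guiding a future sample size. That tempers the point but does not remove it. The Summary sentence is explicit about its purpose, and nothing in section 11 supplies a different target difference.

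Several stronger readings are tempting and are not supported.

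- A reader might infer that the precision claim in section 11.2 is false. It is unquantified. The sentence concerns whether a relevant effect remains plausible and sets no threshold that 0.66 SD could be shown to miss. If a one-sided 80% limit is meant (an assumption), the distance from the estimate to the limit is about 0.28 SD, which could inform a decision on whether to proceed. It would still not make the point estimate safe for sizing.
- A reader might infer that a poor estimate would end the programme, or that this calculation is the main output. Section 4 makes recruitment, eligibility, retention, attendance and delivery the primary objective. None of its Go/Review/Stop limits uses the effect estimate.
- A reader might infer that the SD will be used without allowance for its own error. The protocol does not say how the SD will enter, and taking it from this study is sound. With 36 df its 95% limits are 0.81 and 1.30 times the estimate.
- A reader might see a contradiction between cognition as primary outcome in the Summary and the choice of measure left open in section 4. Fixing the domain while leaving the instrument open (SIB or DLD) is coherent.

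Baseline adjustment would narrow the interval, to about 0.47 SD at an assumed correlation of 0.7, but section 11.1 specifies an unadjusted difference.

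**Conclusion.** The concern holds in this limited form. As written, the Summary makes the observed difference an input to the definitive sample size with no alternative target named, and the precision available for that purpose is about ±0.66 SD, or ±0.57 SD at best. For true effects of 0.3 to 0.5 SD, well over half of such studies would give a sample size wrong by more than a factor of two in one direction or the other: 35% + 39% = 74% at 0.3 SD and 26% + 33% = 59% at 0.5 SD.

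The half-widths follow from the protocol's own numbers and do not depend on the true effect. The mis-sizing frequencies rest on the assumed effects, on 19 completers per arm and on no clustering. The point should be corrected, but it is secondary to the recruitment and retention objectives and does not affect the progression criteria or the conduct of this trial.

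**What to change.** In the Summary and section 11.1, state that the definitive trial will be sized on an important difference justified in advance on the chosen measure, not on the difference observed here. State that this study will supply the SD, the retention rate and, with caution, the ICC.

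In section 11.2, replace the adequacy statement for effect size with the expected 95% half-width (about 0.66 SD at 38 completers, unadjusted). Alternatively, state the confidence level and the relevant effect that the confidence interval approach will use.

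The cost is wording only, with no extra participants, visits or procedures. The stated precision for the effect will look less favourable than the present text suggests.

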# **3** Background and Rationale

Dementia is highly prevalent in people with Learning disabilities (LD) when compared to the general population, with research finding that it is almost five times higher (1) and people with Down's syndrome having a 90% risk of developing dementia in their later years (2). Dementia is therefore a significant cause of mortality (3). Cognitive Stimulation Therapy (CST) has a strong evidence base in terms of benefits for people with dementia in relation to cognitive function and quality of life (4). In the UK, NICE guidelines (5) recommend that everyone with mild to moderate dementia should be offered the opportunity to participate in a group CST programme. The evidence base however does not include studies on the effectiveness of CST in LD, and CST groups are therefore not routinely offered at present to those with ID, as there is no data that suggest it will be effective in this population. Research suggests that CST not only improves cognitive function and quality of life in people with dementia (6) but that it is also cost effective and has comparable efficacy to anti-dementia medication (7). The CST intervention is delivered in a group, typically 2 sessions a week of 45 minutes each over a period of 7 weeks (6). The intervention involves activities such as naming people and objects, word association, number and word games and discussion of current affairs. It uses a range of evidence-based methods such as errorless learning, reality orientation and multi-sensory stimulation (8,9). The benefits of CST could be linked to the activation of neuronal networks associated with cognition such as memory and language (10). It is thought the social interaction involved in the groups also helps in developing new semantic links which could also be associated with the improvement of language in the people who attend the groups (11).

Evidence from one pilot study investigating the effectiveness of group CST in improving cognition, adaptive functioning and quality of life compared to treatment as usual (12) in 25 participants with Down's syndrome found improvement in cognitive functioning at three months in the treatment group in comparison to the control group. Both groups showed an improvement in quality of life scores after three months in comparison to their pre-treatment scores, but this was not significantly different between the groups. The study showed that CST can be adapted for people with ID and that it would be valuable to explore this further in a population with comorbid ID and dementia. An additional feasibility study has also been conducted on individualised CST (iCST) by Ali et al. in 2019

(13). It explored CST being delivered on an individual basis by a family member or other informal care giver of the individual with ID and dementia. The study found that iCST was feasible and acceptable in this population; however a key limitation was that adherence to the treatment protocol was low by the carers. Group CST could therefore be considered a more optimal mode of delivering CST as the groups would instead be run by professionals in the Learning Disabilities teams.

The lack of evidence based treatments for dementia in people with ID is particularly concerning given the high incidence, prevalence, early onset and mortality in this group (1, 3, 14, ). Currently there is only medication offered as a treatment for this group however the evidence for the effectiveness of this is also scarce and people with LD may be more prone to side effects (16). Whilst there is no or limited access to group CST for people with LD, in the general population it is the only evidence based non-pharmacological treatment available and has been proved to benefit cognition and quality of life and is cost effective (6,7). This health inequality urgently needs to be addressed, therefore it is necessary to explore how this evidence based psychosocial intervention might benefit people with LD and comorbid dementia. As iCST in the general population is not as established or evidence-based as group CST it appears that group CST should be explored for equity of treatments for those with LD.

## 3.1 Assessment and Management of Risk

There will be no invasive tests or procedures that will be included above standard care. All the assessments will be based on standardised questionnaires. The intervention is not invasive.

The table below summarise the risks and mitigations of all tests above standard care that are being performed in a table:

Intervention	Potential risk	Risk Management
Group Cognitive Stimulation Therapy	Distress to participants	If participants are distressed by activities, the session should be terminated and reassess with them their willingness to continue taking part in the study.
Administration of cognitive tests	Distress to participants	If participants are distressed, the session should be terminated.

# 4 Objectives

Primary:

To determine the feasibility of recruitment to a randomised controlled trial of group CST by examining the ability to recruit sufficient participants, number of eligible participants, willingness of clinicians to recruit participants, and willingness of participants to be randomised; drop-out rates, adherence and fidelity and acceptability of the intervention, appropriateness of the outcome measures and feasibility of collecting data for both clinical and economic evaluation.

1. Feasibility of recruitment will be ascertained from:

- a. Adequate recruitment, defined as the number recruited to the trial. Go: At least 38 participants recruited to the trial, Review: 25-37 participants recruited to the trial, Stop: Less than 25 participants recruited to the trial.
- b. Recruitment of eligible participants, defined as the percentage of participants recruited to the trial from those eligible. Go: At least 75% of eligible participants recruited, Review: 50-74% of eligible participants recruited, Stop: <50% of eligible participants recruited.
- c. Eligibility, defined as the percentage of participants eligible from those approached. Go: At least 75% of approached participants are eligible, Review: 50-74% of approached participants are eligible, Stop: <50% of approached participants are eligible. Both the numerator and denominator are important here if the denominator is too large it may be that the recruitment strategies need to be refined to streamline recruitment, the numerator being too small may indicate that the eligibility criteria need to be reviewed.

- d. Willingness of participants to be randomised will be assessed by establishing the percentage of potential participants that refuse due to not wanting to be randomised and trial processes.
- e. Retention, defined as the number of participants completing the trial from those recruited. Go: At least 75% of recruited participants complete the trial, Review: 50-74% of recruited participants complete the trial, Stop: <50% of recruited participants complete the trial. compare proportion of treatment and control group who return for follow up assessments.
- 2. Acceptability and adherence of CST will be ascertained from:

a. Overall attendance amongst the CST group participants. Confirmation of adequate attendance amongst sessions delivered. Go: 75% of all intervention sessions attended, Review: 50-74% of all sessions attended, Stop:< 50% of sessions attended.

b. Confirmation of adequate delivery of sessions. Go: 75% of all intervention sessions delivered, Review: 50-74% of all sessions delivered, Stop:<50% of sessions delivered.

c. Acceptability demonstrated through qualitative Interviews with 10 CST participants purposively sampled plus 10 carers and 10 group facilitators (two per NHS site).

Secondary:

1. To assess the fidelity of delivery of the groups by;

a. Recording the number of group CST sessions completed by each participant and level of engagement in the sessions measured using CST participation forms developed alongside the CST manual.

b. Exploring the quality of the intervention delivery according to the recordings and facilitators reflections on delivery fidelity. We will be using a validated CST adherence checklist in order to assess fidelity.

2. To assess the suitability of study outcome measures and determining the primary outcome measure for a future larger RCT:

a. Analysis of completion/ response rates of outcome measures with confirmation these can be collected from the participants.

Go (for each measure): At least 85% of participants fully complete the outcome measure at each time point, Review: 70 - 84% of participants fully complete the measure at each time point, Stop: <70% of participants fully complete the measure at each time point.

b. Examining whether the measures are sensitive to change as a result of the intervention will be established by the preliminary analysis proposed in the statistical analysis section.

3. Collecting resource use information.

Feasibility of collecting resource use data for generating cost information for use in an economic evaluation, including intervention costs. This uses a modified version of the Client Service Receipt Inventory (CSRI) to capture information on health and social care resource use relevant to this population and context, such that published unit costs from NHS Reference Costs and the Personal Social Services Research Unit (PSSRU) Health and Social Care unit costs could be applied to calculate costs in a future full RCT. The modified CSRI is being prepared by the health economist in collaboration with PPI collaborators, clinicians, and other trial team members, and includes information on primary and community health care, medications, routine and emergency hospital care and use of personal social services, provided either by the state or funded privately, as well as financial or related impacts on carers.

